4.3 Rationale for Study Design

An alternative design would involve randomization of clients and providers within the agencies. Although that could avert potential confounds attributable to differences between agencies, we considered the risk of contamination – and, thus, a threat to internal validity – from such a design to be too probable. While an agency-level randomization may be subject to confounding as well, we will match the agencies on key variables before randomization to increase control over potential treatment confounds and we will use appropriate analytic models to account for this potential confounding (see Data Analysis). We also considered either: 1) not including a control arm; or 2) providing a more potent control arm, but considered the present design one that would allow for more convincing conclusions about the effects of ATTOC vs. current practice. Thus, we viewed the proposed design to be the ideal balance between internal and external validity.

4.4 COVID-19 Adjustments

Due to the COVID-19 pandemic, all sessions are being done remotely at this time. If a client reports abstinence, they will be asked to come to the office to do a CO reading. They will be compensated an additional \$10 if they travel to the office. This applies to Week 12, 24, 36, and 52 sessions.

4.5 COMHAR Clinic

Due to the COVID-19 pandemic, the recruitment and enrollment process had to be adjusted since the clinic is largely running via telemedicine. Clinic leadership will send a letter informing their clients of the study and what it entails. A research assistant's number will be listed if they wish not to be contacted. After two weeks, the research team will begin to reach out to clinic clients to conduct an eligibility screen. If the client is eligible and wants to participate, a time will be scheduled for the baseline session. A CO reading will not be conducted at baseline. The consent will be read aloud in its entirety to patient participants. The baseline session will be conducted remotely (over the phone or video chat) and participants will then give their verbal consent. The research staff member will note in the consent form that the participant affirmed their consent, as well as the date of the consent. The consent document will also be sent to participant, either over email or through the mail. For clinic personnel participants, reviewing the consent form will be completed using a RedCap survey. Once the consent is signed, a research staff member will electronically sign it. Staff will email the survey link to them and the subjects will indicate within the RedCap survey if they wish to participate and will then be prompted to enter their First and Last name and sign the form using their finger or mouse. Subjects will be able to download their signed version of the form from RedCap, and staff will also download a version to

be saved to the electronic regulatory binder on our secure server, or, printed and placed in our physical binder. In order to make things more convenient and efficient, the study questionnaires for clinic personnel enrolled in the study will be on REDCap. A CO reading for clients will not be collected at baseline. Participants who report abstinence at week 12, 24, 36, or 52 will be asked to come to our office for a CO reading. The CO reading will be done outside and the staff will try to maintain social distance as much as possible. The participant will be given an additional \$10 for travel compensation. The training session for the personnel will be conducted over video chat (could be split up into two sessions on different days) before the recruitment period is over. These same procedures will be used at the Merakey clinic.

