4.1 General Design

This cluster-randomized trial will be conducted with 14 Philadelphia CMHCs, 7 randomized to ATTOC and 7 to usual care (UC). Following randomization, study staff will visit sites to recruit clinic personnel and clients over a 4 to 6 week period. Those eligible will complete informed consent and HIPAA forms and a baseline assessment to establish pre-intervention levels on all measures (baseline). After 4-6 weeks, the ATTOC intervention will be implemented over 9 months, from Week 1 to Week 36 (with UC at the control sites). Two mid-intervention assessments (Weeks 12 and 24) will allow for performance feedback (see Outcomes Data) and mediational analyses. Week 36 (end-of-treatment; EOT) and 52 (3-months post-EOT) assessments will allow for evaluation of changes on outcomes between groups over time. All measures will be conducted at the respective CMHC

(or over the phone if necessary) and 7-day point prevalence smoking cessation will be verified using a breath carbon monoxide (CO) monitor (abstinence = < 8ppm; [93]). Figure 1 illustrates the study design.

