Once sites are randomized, we will use a 4 to 6 week window for subject recruitment. This will allow study staff to recruit in-person for multiple days and across several weeks to ensure that we access all site personnel and a representative sample of clients. We have experience recruiting in clinic settings [59, 71] and have 2 ongoing studies that follow such procedures (R01 CA165001; R01 DA033681). If the 4-6 week period is not sufficient time to recruit a participant sample, the Principal Investigator reserves the right to lengthen the recruitment window by 4-6 weeks. The Principal Investigator may also need to under-enroll clinic personnel or client participant groups at certain sites due to organizational constraints. This under-enrollment will be supplemented at larger clinics by over-enrolling participants at other sites. In order to prevent possible retribution against clinic

personnel on the part of clinic leadership, we will not disclose the enrollment decisions of clinic personnel, and we will offer smoking cessation resources to the clinic.

To recruit personnel, we will use staff meetings, electronic and written communication, and hold study-specific meetings. To recruit clients, as done now (R01 CA126969), but modified as needed upon advice from the Community Advisory Council, our Research Assistants (RAs) will assess every scheduled client for interest and eligibility using clinic schedules to approach clients prior to or after appointments. We post program flyers and brochures in clinics as well. Participants who are eligible and interested in the study will be scheduled for an intake session. To assess external validity, eligible personnel and clients who refuse entry will be compared to those who enroll based on available data (e.g., smoking status, years employed, nature of SMI).

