Client/Personnel Eligibility Screen		X											
TREATMENT													
ATTOC			X	X	X	X	X	X	X	X	X	X	
UC			X ²										
MEASURES													
COVARIATES													
Demographics, Smoking History & FTND (S-KAP, S-KAS)		X				X			X			X	X
Client Psychiatric History ²		X											
Client COVID-19 Questionnaire		X											
Clinic/Clinician Change (The Dashboard)			X	X	X	X	X	X	X	X	X	X	
MEDIATORS													
Personnel Knowledge and Attitudes (S-KAP)		X				X			X			X	X
Client Knowledge and Attitudes (S-KAS)		X				X			X			X	X
TREATMENT DATA													
ATTOC Intervention Adherence (The Dashboard)			X	X	X	X	X	X	X	X	X	X	
ATTOC Change Plan			X			X							
ATTOC Environmental Scan			X			X							
ATTOC Communication Plan			X			X							
OUTCOMES													
Adherence to TUD Guidelines (S-KAP)		X				X			X			X	X
Adherence to TUD Guidelines (S-KAS)		X				X			X			X	X
Adherence to TUD Guidelines (Client Prescription Data) ²												X	X
Client Smoking Status (CO Form)		X											
Client Smoking Status (TLFB)						X			X			X	X
Client Mental Health (BASIS-R)		X				X			X			X	X
Client QOL (SF-12)		X				X			X			X	X
Client Hospitalization Form ²												X	X
Treatment and Client Costs		X										X	X

¹ Activities associated with this timepoint may occur any time within the 4-6 week period directly preceding Week 1.

² Data provided by request from Community Behavioral Health (CBH)

³ This is a one-day training lead by [name] and/or [name].

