6.3 Session Windows

Intervention treatment sessions for clinic personnel will occur +/- 1 week from the study timeline date to account for scheduling needs of clinics and trainers. In-person ATTOC sessions at Week 1 and 12 may be scheduled +/- 2 weeks from the study timeline date as travel arrangements must be made for the UCSF study team. If a personnel participant at an ATTOC randomized clinic is not available to attend any interventional study session (Weeks 1-36), the intervention will not be repeated for individuals.

Personnel participants who miss an assessment session or are unable to complete an assessment within the allotted session time are afforded a +/- 1 week study window to complete the assessments by phone. If there are extenuating circumstances that would cause personnel participants to miss a study session (e.g., end of an employment period), personnel sessions may be

completed earlier than the +/- 1 week session window. All client participant assessments will have a window of +/- 1 week to complete treatment and outcomes assessments for weeks 12, 24, 36, and 52. Participants may choose to complete the assessments in person or by phone.

Session windows may be extended with prior authorization from PI at his discretion. Session window extensions will not be considered reportable deviations.

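### At COMHAR and Merakey the staff training is scheduled inside the recruitment period, so some baselines may be taken after training although the plan defines baseline as pre-intervention

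*Combined protocol and SAP*

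**What the plan says.** Section 4.1 (General Design) has participants complete "a baseline assessment to establish pre-intervention levels on all measures (baseline", and then gives the order of events: "After 4-6 weeks, the ATTOC intervention will be implemented over 9 months, from Week 1 to Week 36". Footnote 1 to the schedule table in section 6 (Study Procedures) says of the baseline time point: "Activities associated with this timepoint may occur any time within the 4-6 week period directly preceding Week 1". Section 6.2.2 makes staff training the Week 1 event in both arms: one day at usual care (UC) clinics and a three-day on-site visit at ATTOC clinics.

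Section 4.5 (COMHAR Clinic) changes the order for a clinic working largely by telemedicine. The personnel training is to be held over "video chat (could be split up into two sessions on different days) before the recruitment period is over". Client baselines are arranged individually: "If the client is eligible and wants to participate, a time will be scheduled for the baseline session". A second clinic is brought under the same rule: "These same procedures will be used at the Merakey clinic".

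Two general provisions bear on timing. Section 5.5 states "Once sites are randomized, we will use a 4 to 6 week window for subject recruitment" and lets the investigator lengthen that window by another 4 to 6 weeks. Section 6.3 states "In-person ATTOC sessions at Week 1 and 12 may be scheduled +/- 2 weeks from the study timeline date".

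**The concern.** Sections 4.1 and 6 put every baseline before training. Section 4.5 puts training before the end of recruitment and does not require baselines to be finished first. Anyone enrolled in the gap would carry a baseline labelled pre-intervention that was measured after the clinic's staff had been trained.

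For staff the effect is direct, because the S-KAP asks about the knowledge, attitudes and practices that the training addresses. For clients it is indirect: they are not trained, so an S-KAS baseline could move only if they had already had contact with trained staff.

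The plan uses baseline to control for differences between UC sites (6.1.1), as the starting point for change over time (4.1) and as the starting point for mediator change (7.2.1, Exploratory Aims). A baseline that already contains some training effect understates change at that clinic and distorts any adjustment that relies on it.

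**Working it through.** The plan states no figure on this point, so there is none to reproduce. The check is of sequence, followed by simple bounds.

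**1. Order of events**
- General rule (4.1; section 6, footnote 1): recruitment and baseline, then Week 1.
- Week 1 content (6.2.2): staff training in both arms.
- COMHAR and Merakey (4.5): staff training before recruitment ends, with client baselines booked as people enrol.
- Safeguards: no section closes enrolment at training, requires baselines to be complete by then, or flags or adjusts for later ones.

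The two orders agree only if everyone at these clinics happens to be assessed before the training. The text allows that but does not require it. Section 4.5 also delays client contact until two weeks after a letter. If that wait counts toward the 4 to 6 week window, client enrolment falls in its later part.

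**2. Ceiling on the number affected** (sample sizes from 5.2)
- Clinics: 2/14 = 14.3%.
- Staff: 280/14 = 20 per clinic; 2 × 20 = 40.
- Clients: 700/14 = 50 per clinic; 2 × 50 = 100.

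Only those assessed after training are affected. The documents do not give that number.

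**3. Where baseline enters the analysis**
- Aim 1 and Aim 2 primary outcomes are levels at weeks 36 and 52 (7.2.1). Without baseline in the model, a late baseline does not alter these contrasts.
- Covariates are optional: variables related to arm or to follow-up completion at p < .10 may be added (7.2). If baseline adherence is added, the contrast is affected.
- Change over time (4.1) and the exploratory mediation analysis (7.2.1) start from baseline.

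**4. Illustrative size, staff S-KAP only**

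Let d be the rise in the 5-point adherence score already present when a late baseline is taken, and f the share of a clinic's staff assessed late. Both are assumptions. The upper d of 0.51 is the 3-month mean change quoted in 7.1. The middle value of 0.32 is the detectable increase at ICC = 0 in 7.1, used only as a midpoint. The lower value of 0.11 has no source in the plan.

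- Rise in the clinic's baseline mean = f × d.
- Rise in the arm's baseline mean, if both clinics are among its 7 = (2/7) × f × d.

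| d | f | Clinic | Arm |
|---|---|---|---|
| 0.11 | 0.25 | 0.03 | 0.008 |
| 0.32 | 0.50 | 0.16 | 0.046 |
| 0.51 | 0.75 | 0.38 | 0.109 |

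The arm figure therefore runs from about 0.01 to 0.11. A change-from-baseline contrast would move by that amount against the arm holding the clinics. A baseline-adjusted contrast would move by roughly that amount times the baseline slope, so by half of it at an assumed slope of 0.5. With one clinic in each arm the shifts partly cancel. No client figure can be given.

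**The case against.** The strongest reply is that this is a local wording conflict with little reach. The primary outcomes are levels, covariates are optional and the mediation analysis is exploratory. The number affected could be zero for staff: their forms run separately in REDCap and could be finished before training while client calls continue. This stands as a limit on the harm. It does not reconcile the sections, and the plan has no means of showing how many baselines were late.

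A reader might go further in three ways that the documents do not support.

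- **That the ATTOC intervention has begun before baseline.** Section 4.5 names no arm. One session that may be split over two days resembles the 1-day UC seminar more than the 3-day ATTOC visit. The UC seminar is still that arm's Week 1 event, so a later baseline is still post-training.
- **That the bias is 11 to 21% of the detectable difference.** This comes from applying the 14% pilot increase (2.2) to the mean of 2.36 (7.1): 0.14 × 2.36 = 0.33; 0.33 × 2/7 = 0.094, or 0.047 with a slope of 0.5; divided by 0.44, 21% or 11%. It needs every staff member at both clinics to be assessed after training, and both clinics in one arm. The pilot figure is for complex behaviours after a multi-component programme measured two months post-treatment, not one session shortly before a survey. The chance that the clinics share an arm would be 2 × (7/14 × 6/13) = 0.46 under simple allocation, but 4.2 matches sites on size and motivation, so it cannot be derived.
- **That sections 5.5 and 6.3 create the same defect trial-wide.** Footnote 1 ties the baseline window to Week 1, so it can move with Week 1, and a longer recruitment period can equally delay training. These sections leave an overlap possible; only 4.5 schedules training inside recruitment.

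**Conclusion.** The contradiction holds: section 4.5 cannot be followed as written with any assurance that baseline is pre-intervention, as 4.1 and the schedule require. It concerns 2 of 14 clinics and at most about 40 staff and 100 clients, with an unknown number actually late and the arm unstated.

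The unadjusted week 36 and 52 contrasts are not biased by it. Baseline-adjusted, change-over-time and exploratory mediation analyses can be, in a direction set by the arm. If the clinics are UC, UC change is understated and the comparison tilts toward ATTOC; if they are ATTOC, the reverse.

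The 0.01 to 0.11 range for the arm's baseline mean rests on both clinics sharing an arm, 25 to 75% of staff being late, and an assumed training effect of 0.11 to 0.51. The top end requires the full 3-month change in the cited residential study to be present before the survey. The point is worth correcting because the remedy is cheap; it does not undermine the primary result.

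**What to change.** 1. Reconcile section 4.5 with 4.1 and footnote 1 in section 6: at each clinic, every personnel baseline and the client baselines must be complete before the personnel training session. The leadership call in 6.1.2 may go ahead as planned.
2. Add to section 6.3 that a Week 1 session moved early may not precede the close of baseline at that clinic.
3. Where training has already taken place, flag each participant whose baseline date is on or after the training date, and report the count by clinic and arm.
4. Do not use flagged S-KAP or S-KAS values as pre-intervention values in adjusted, change or mediation analyses. Keep those participants' week 36 and 52 outcomes, state how the missing baseline is handled, and add a sensitivity analysis that includes the flagged values.

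The cost is a short addition to each of 4.5 and 6.3, a date comparison in the data system and one sensitivity analysis. Training may slip by a week or two at a clinic that recruits slowly. A few baselines are lost, selectively from late enrollees, which is the reason for the sensitivity analysis.

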4.6 Study Timeline

Providing ATTOC or UC will occur sequentially from Months 7-36 (end of Year 3): 3 sites in months 7-16, 4 sites in months 17-26, 4 sites in months 27-36, and 3 sites in months 37-48. Data collection, analysis, and reporting will occur in Years 4-5 (see Table 3).

Table 3. Study Timeline

Tasks/Months	1	12	24	36	48	60
Refine/test DMS, Train Staff (1-6)	X-X					
Recruitment/baselines (7-36)		X	-----	X		
Treatment (7-36)		X	-----	X		
Outcome assessments (12-48)			X	-----	X	
Analysis/manuscripts (48-60)					X	--- X

4.7 Study Measures

Screening

- **Community Mental Health Clinic Eligibility Screen:** The assessment will be completed by a CMHC leader such as a CEO and contains questions that will assess eligibility criteria as well as organizational readiness (the latter will be accomplished with the ORIC). The results of this assessment will be taken into account during clinic intervention randomization.
 - **Organizational Readiness for Implementing Change (ORIC):** This psychometric assessment measures change commitment and change efficacy [92] in prospective CMHCs. This assessment includes a scale with 12 questions.
- **Clinic Leadership Informed Consent Acknowledgement:** A designated clinic leader will review the informed consent and will complete the inform consent acknowledgement form. This form was devised to help ameliorate possible concerns regarding undue coercion surrounding clinic personnel recruitment. This form is included for review by the personnel participants during the informed consent process.
- **Client and Personnel Eligibility Screen:** These brief assessments contain questions based on inclusion and exclusion criteria to ensure study eligibility.

Covariates

- **Client Psychiatric History:** Among clients, we will collect self-reported data on past and current psychiatric conditions/diagnoses, duration of illness, and lifetime frequency of psychiatric hospitalizations. Psychiatric diagnosis will be confirmed via data requested from CBH.
- **COVID-19 Quitting Experience Questionnaire:** The purpose of this survey is intended to capture the participant's experience quitting smoking during the COVID-19 pandemic. The survey will be administered at baseline for personnel. The survey will include 24 questions recommended by the NIH for research pertaining to COVID-19, 11 questions related to smoking behavior and the pandemic formulated by staff, and the PHQ-2 and GAD-2 measures for depression and anxiety symptoms (4 questions total).

Mediators:

- **Smoking Knowledge, Attitudes, and Practices (S-KAP):** This survey is composed of 5 scales that assess systemic and cultural barriers to smoking cessation. These scales measure clinician practices, knowledge regarding smoking risks, barriers, attitudes and efficacy [103]. Systemic barriers include provider: 1) access to resources to treat TUD; 2) level of knowledge to treat TUD; 3) implementation of smoking cessation policies such as a smoke-free campus; and 4) use of the EHR to document and track client smoking and treatment. Cultural barriers include provider beliefs about: client interest in smoking cessation, client ability to quit smoking, client ability to understand the benefits of smoking cessation, client mental health consequences from cessation, and smoking cessation treatment being their responsibility. These Likert-type measures are sensitive to change following implementation of ATTOC [18] and have good psychometric qualities [94, 103]. This survey will also be used to measure outcomes data (items measuring the rate of: asking clients about smoking, advising them to quit, providing assistance with quitting, and arranging visits to track progress; a total adherence score can be calculated [18].)
- **Smoking Knowledge, Attitudes, and Services (S-KAS):** This survey is essentially a client version of the S-KAP and will be used to measure systemic and cultural barriers to smoking cessation from the client's perspective. The survey

contains 4 Likert-type scales that measure client knowledge regarding smoking risks, attitudes about quitting smoking as related to the clinic setting, and assessments of clinician and program services, respectively [105].

Treatment Data:

- **ATTOC Intervention Adherence Tool (“The Dashboard”):** This web-based tool is used by the study team to track and monitor compliance and progress on the 10 ATTOC steps – on an organizational and on an individual (clinician) level. This adherence measure is used to determine the level of compliance with ATTOC steps so that variability across sites in the implementation of ATTOC can be included in analyses and to guide performance feedback. The dashboard is a visual figure with a numeric indicator using red (no movement), yellow (some progress), and green (completed) colors that enables staff to see progress on key metrics of change. Data are gathered through staff self-report and chart reviews, study measures, and the environmental scan. On an organizational level, examples of metrics include: the selection of a site champion, the use of change and communication plans, the implementation of change plans, additional staff training, the provision of TUD treatment (counseling, referrals, pharmacotherapy), the establishment of a smoke-free campus or progress in establishing smoking restrictions, use of no-smoking signage, inclusion of TUD treatment within SOPs, and provision of TUD treatment brochures. On an individual level, examples of metrics include: the provision of TUD counseling, number of referrals to smoking cessation treatment programs including the Quit-line, and the provision of pharmacotherapy. This dashboard assessment reflects metrics of overall organizational and individual clinician change and is used as a covariate in analyses of study aims and to guide performance feedback to clinic leadership, site champions, and clinicians. We will also include a measure of fidelity to determine whether the ATTOC model was implemented as intended. This measure includes: attendance at on-site training sessions, logging onto the ATTOC program training website, and participation in training teleconference/video calls. The fidelity measure, analogous to a measure of treatment dose, will be expressed as a proportion of the number of training hours received and used as a potential covariate. All personnel participants are expected to interact with the Dashboard and update the metrics. The chosen site champion will be responsible for reviewing the metrics prior to scheduled training sessions and will summarize the findings for the group.
- **ATTOC Change Plan:** This instrument assesses the following: 1) agency goals 2) identifying key clinic leadership and champions 3) environmental scan 4) recording the change plan drafting process 5) recording the communication plan drafting process 6) setting client goals 7) setting staff goals 8) setting environmental goals 9) documenting clinic policy changes 10) identifying supportive activities to sustain organizational change. Once the leadership group and tobacco champion are identified, these individuals are tasked with meeting regularly (as the group deems fit) to hone the Change Plan over time. The tobacco champion serves in a secretary capacity to record meeting minutes and/or progress notes that will be presented to the ATTOC consultation team for review.
 - **ATTOC Environmental Scan:** An Environmental Scan provides a structured tool to assess: the strengths, weaknesses, opportunities, and threats to the new business plan or idea. The ATTOC approach applies this tool in order to assess an agency’s preparedness to address tobacco, including past successes and efforts already underway on this issue. The Environmental Scan can be used to assess changes in organizational preparedness and inform potential improvements during the course of planning, implementation, and sustaining changes. This can assist the agency as they work on their change plan. The Environmental Scan focuses on four key areas of the ATTOC intervention:
 - Agency’s campus and inside the buildings / Environmental Tobacco Control Efforts
 - Client Assessment and Treatment
 - Staff Competencies, Smoking, and Attitudes
 - Tobacco-Related Policies for Clients, Staff, and the Agency.

This Environmental Scan enables the ATTOC consultation team to objectively document current tobacco-related activities and to subjectively assess preparedness for further improvements. In order to complete this form and the evaluation, the assessment process includes conducting a “walk through” of both the inside and outside of your agency, speaking with staff and clients, and also reviewing existing clinical charts and policies.

Each of the four key areas receives a preparedness rating ranging from a “1” (not prepared) to “5” (highly prepared). For each area, there is a preparedness rating “key” providing a short description of general characteristics that constitute each rating. This key can serve as a guide for the consultant team when assigning preparedness scores.

At the conclusion of the Environmental Scan, an overall client, staff, environment, and agency ratings are given. The ATTOC Consultant team rejoins the Leadership Team to discuss the agency’s observed preparedness to address tobacco and to begin to formulate the agency’s change plan to identify specific objectives for tobacco assessment, treatment, and policies.

- **ATTOC Communication Plan:** Step 5 of the ATTOC Approach addresses the importance of supporting the Change Plan by developing a Communication Plan to facilitate internal and external communication needs. It is a way to communicate with stakeholders, determine channels for feedback, and to communicate new policies and procedures. This tool is used to familiarize the personnel participants with current clinic communication processes and resources and provides a framework for designing a new plan of action in this area.

Outcomes Data:

- **Client Prescription Data:** Client participant prescription data (for cessation medications or NRTs) will be requested from CBH.
- **Time Line Follow-Back (TLFB):** This assessment utilizes a structured interview method to assess smoking rates. Using a calendar with sufficient days from the prior assessment time point, study staff work with the participant to formulate a clear picture of whether abstinence was achieved each day. The purpose of the interview will be to reconstruct the participant's smoking practices, on a daily basis if possible. Beginning with current smoking habits, the staff member prompts the participant to recall previous smoking rates in a backward chronological fashion.
- **CO Form:** This assessment collects the CO reading (in parts per million) as well as smoking rate in the 24 hours preceding data collection and the time since the participant's last cigarette.
- **Revised Behavior and Symptom Identification Scale (BASIS-R):** Clients will complete the Revised Behavior and Symptom Identification Scale (BASIS-R), a 24-item assessment of mental health functioning [108] that yields a total score and subscale scores for: depression, interpersonal relationships, self-harm, emotional lability, psychosis, and substance abuse.
- **Client Hospitalization Assessment:** We will assess the frequency and duration of any illness-related in- client hospitalization. This self-report measure will be confirmed via data requested from CBH.
- **Short-Form Health Survey (SF-12):** This survey will assess physical and mental QOL of client participants [109, 110].
- **Treatment and Client Costs:** These costs will be estimated by multiplying the counts of resources used by the unit costs of those resources (the resource costing method [111, 112]), which summarizes the health care services used from the perspective of society (e.g., TUD treatment delivery time), not only protocol costs. ATTOC direct costs will be considered as will non-study medical services costs, recorded on a validated scale [113].

See Table 4 under Study Procedures for study events and associated measures.

